^l Concomitant medications will be identified and recorded along with their indication as described in [Protocol Section 6.5](#).

^m Symptom-directed PEs will be conducted as described in [Protocol Section 8.3.3](#).

AV7909 Anthrax Vaccine

IND 014451

Protocol EBS.AVA.210, Version 3.0 (28 October 2019)

ⁿ Blood samples for TNA assessment on Day 1 will be collected in the morning following randomization. Those on Day 37 will be collected after the final dose of ciprofloxacin has been administered. A TNA sample will also be collected if EWV occurs within the visit window of Day 37 as described in [Protocol Section 8.1.8](#).

^o Ciprofloxacin doses (500 mg po q 12 hr) will be administered as described in [Protocol Section 6.1.5](#) with the first dose being administered on Day 4 when the cipro PK group enters their first PK session.

^p Ciprofloxacin dose compliance will be managed as described in [Protocol Section 6.4](#).

^q Blood samples for assessment of ciprofloxacin concentrations will be collected as detailed in [Protocol Section 8.4](#).

^r Vaccinations with AV7909 will be administered as described in [Protocol Section 6.1.4](#).

^s All Participants will be provided with an e-diary for post vaccination follow up along with a thermometer and an injection site reaction measurement tool. Participants in Group 1 and 2 will be provided with an e-diary for antibiotic compliance. All participants will be trained on the use of these tools and the e-diaries as described in [Protocol Section 8.3.5.1](#).

^t Staff will begin reviewing the e-diaries on Day 6 and will review them at regular intervals thereafter.

^u AEs will be collected at all clinic visits through Day 51/EWV as described in detail in [Protocol Section 9](#).

^v AEs, SAEs and potential AESIs will be collected during the Safety Follow-up Telephone Calls (see [Protocol Section 8.1.7](#)).

^w Serum samples for TSH & autoantibody testing will be collected from all participants and tested as described in [Protocol Section 8.3.2](#) (ie, at Day 1, Day 51, and at EWV if the subject received at least one vaccination). Additional samples for TSH & autoantibody testing may be requested (eg, based on participant report(s) of a potential AESI); blood draws for additional TSH and/or autoantibody testing should be performed as part of an unscheduled visit.

8.1.2.1. Group 1A: Day 3 – Overnight Stay # 1

1. Admit to the clinic for overnight stay #1.

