^q Staff will begin reviewing the e-diaries on Day 5 and will review them at regular intervals thereafter.

^r AEs will be collected at all clinic visits through Day 51/EWV as described in detail in Protocol Section 9.

^s AEs, SAEs and potential AESIs will be collected during the Safety Follow-Up Telephone Calls (see Protocol Section 8.1.7).

^t Serum samples for TSH & autoantibody testing will be collected from all participants and tested as described in Protocol Section 8.3.2 (ie, at Day 1, Day 51, and at EWV if the subject received at least one vaccination). Additional samples for TSH & autoantibody testing may be requested (ie, based on the participant's report(s) of a potential AESI); blood draws for additional TSH and/or autoantibody testing should be performed as part of an unscheduled visit.

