^d Vital signs will be administered as described in [Protocol Section 8.3.4](#).

^e Pregnancy tests (serum and/or urine) will be administered to all WOCBP as described in [Protocol Section 8.3.2](#). Serum pregnancy test will be performed at Screening visit for WOCBP, while urine pregnancy tests for WOCBP will be required before each vaccination. At Screening visit only, FSH test will be performed for postmenopausal women.

^f Hematology will be conducted as described in [Protocol Section 8.3.2](#).

^g Serum chemistry will be conducted as described [Protocol Section 8.3.2](#).

^h Urinalyses will be conducted as described in [Protocol Section 8.3.2](#).

ⁱ Urine drug screens will be conducted as described in [Protocol Section 8.3.2](#).

^j Concomitant medications will be identified and recorded as described in [Protocol Section 6.5](#).

^k Symptom-directed PEs will be conducted as described in [Protocol Section 8.3.3](#).

^l Blood samples for TNA assessment on Day 1 will be collected in the morning following randomization. Those on Day 37 will be collected in the morning. A TNA sample will also be collected if EWV occurs within the visit window of Day 37 as described in [Protocol Section 8.1.8](#).

^m Vaccinations with AV7909 will be administered as described in [Protocol Section 6.1.3](#).

ⁿ All participants will be provided with an e-diary for post vaccination follow up along with a thermometer and an injection site reaction measurement tool and will be trained on the use of these tools and the e-diary as described in [Protocol Section 8.3.5.1](#).

^o AEs will be collected at all clinic visits through Day 51/EWV as described in detail in [Protocol Section 9](#).

^p SAEs and potential AESIs will be collected during the Safety Follow-up Telephone Calls (see [Protocol Section 8.1.7](#)).

^q Serum samples for TSH & autoantibody testing will be collected from all participants and tested as described in [Protocol Section 8.1.6.3](#) (ie, at Day 1, Day 51, and at EWV if the subject received at least one vaccination). Additional samples for TSH &

AV7909 Anthrax Vaccine

IND 014451

Protocol EBS.AVA.210, Version 3.0 (28 October 2019)

autoantibody testing may be collected based on the safety follow-up phone contact if warranted from participant report(s) of a potential AESI); blood draws for additional TSH and/or autoantibody testing should be performed as part of an unscheduled visit.

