8.1.6.3. Group 3: Day 37 (± 1 d) – Blood Draw for TNA

The Day 37 Visit may shift by ± 1 d.

1. Review e-diary entries with participants, discussing any changes in health status and the use of concomitant medication as well as any vaccination reactions if still ongoing.
2. Review and record AEs.
3. Record concomitant medications.
4. Conduct symptom-directed PE (if necessary).
5. Collect blood sample for TNA assessment.

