8.1.7. Quarterly Safety Follow-up Phone Calls

Following the last scheduled vaccination, the site will conduct quarterly safety follow-ups in which participants are contacted by phone at 3 months (Day 114 ± 14 d), 6 months (Day 205 ± 14 d), 9 months (Day 296 ± 14 d) and 12 months (Day 388 ± 14 d). These phone contacts will be scheduled to key off the participant's actual or, if missed, target Day 23 visit (intended last vaccination day) so that all participants (even those failing to receive both vaccinations but who are followed for safety only) are contacted 3 months after their target Day 23.

The following assessments will be performed over the phone at the 3 months (Day 114 ± 14 d), 6 months (Day 205 ± 14 d), 9 months (Day 296 ± 14 d) and 12 months (Day 388 ± 14 d) contacts:

- Assess and document, AEs, SAEs and potential AESIs (refer to [Section 9.3](#))
- For WOCBP, confirm continued use of an adequate method of contraception and inquire about any possible pregnancies (refer to [Section 9.4](#))
- If an AE, SAE and/or an AESI is reported, record any associated medications
- Review the status of ongoing AEs/SAEs/AESIs to update the resolution status

During the telephone calls, the staff member is to inquire about and record in source documentation any AEs and SAEs occurring since either the Day 51 visit or the previous phone contact. Any occurrence of SAEs will be reported to Emergent immediately as specified under [Section 9.3](#) and followed up per procedures described in [Section 9.7.2](#). If an SAE has occurred, it will be recorded on the AE eCRF with any medications taken also recorded on the appropriate eCRF.

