9.2. Eliciting and Reporting Adverse Events

AEs (including SAEs and potential AESIs) reported spontaneously by the participant and/or in response to an open question from the PI or designee or revealed by observation (eg, during PE

AV7909 Anthrax Vaccine

IND 014451

Protocol EBS.AVA.210, Version 3.0 (28 October 2019)

or from a clinical test result) will be recorded on the AE eCRF if they occurred from the time of the first administration of any IP (Day 2 for Group 2, Day 4 for Groups 1 or Day 8 for Group 3) through Day 51 or EWV, regardless of causal association with the IP. AE reporting is required for any new observation presenting after the first receipt of any IP or for a deterioration of baseline condition (eg, increased severity/frequency). From the signing of the ICF until immediately before the administration of their first IP, only AEs resulting from a study-related procedure will be recorded on the AE eCRF; all other events reported in these time periods will be recorded as signs and symptoms on the Medical History eCRF. If there is any doubt as to whether a clinical or laboratory observation is an AE, the event will be considered an AE and recorded on the AE eCRF. After Day 51 and through the 12-month safety follow-up, AEs, SAEs (meeting definition per [Section 9.1.2](#)) and AEs assessed by the DSMB to be of autoimmune etiology (refer to [Section 8.5](#)), ie, AESIs, will be recorded on the AE eCRF.

Refer to the specific sections on clinical laboratory tests ([Section 8.3.2](#)), PEs ([Section 8.3.3](#)), vital signs ([Section 8.3.4](#)), and e-diary reactogenicity ([Section 8.3.5.1](#)) for details on AE reporting based on participant observation and clinical test results.

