### 8.1.2 All TEAEs

All TEAEs will be tabulated by SOC and PT (in descending order of participant incidence in “AV7909 Total” column).

TEAEs with 5% or more for a PT term in any treatment group will be tabulated by SOC and PT.

All TEAEs will be summarized by SOC, PT, severity, and treatment group. The severity of AEs will be assessed by the PI or designee using toxicity grading (Grade 1 to 4) according to Protocol EBS.AVA.210, [Appendix A](#). All TEAEs will also be summarized by SOC, PT, relationship to study treatment, and treatment group. Participants having the same TEAE more than once will be counted once for each PT and once within each SOC at the maximum severity and relatedness. If the severity/relatedness is missing for one or more of the occurrences, the maximum severity/relatedness of the remaining occurrences will be used.

TEAE summaries will be provided for TEAEs through the Final Study Visit (Day 51) and for all TEAEs through the 12-month follow up , respectively.

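### TEAEs are counted over 50, 48 and 44 days in Groups 2, 1 and 3: add one table from first vaccination, and reconcile the call footnotes and Day 37 lists.

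*Protocol*

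**What the plan says.** **Window.** Protocol Section 9.2 starts AE recording at first product: "Day 2 for Group 2, Day 4 for Groups 1 or Day 8 for Group 3". The safety endpoint in Section 3.2.2 runs from there to Day 51, and SAP Section 8.1.1 programs TEAEs by the date of first exposure to any study treatment. SAP Section 8.1.2 summarises TEAEs to Day 51 and, separately, "for all TEAEs through the 12-month follow up". SAP Section 8.1.3 adds a table of TEAEs with onset before the first vaccination, but no counterpart starts at that vaccination.

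**Safety calls.** The Table 5 footnote (Group 1A) reads "AEs, SAEs and potential AESIs will be collected during the Safety Follow-up Telephone Calls". Tables 6 and 7 (Groups 1B and 2A) say the same: "AEs, SAEs and potential AESIs will be collected during the Safety Follow-Up Telephone Calls". The Table 8 and 9 footnotes (Groups 2B and 3) read "SAEs and potential AESIs will be collected during the Safety Follow-up Telephone Calls". All five footnotes point to Section 8.1.7, which for every participant says "Assess and document, AEs, SAEs and potential AESIs". Section 9.2 sets the eCRF recording rule in the same sense: "After Day 51 and through the 12-month safety follow-up, AEs, SAEs", followed by AESIs. The synopsis and SAP Section 2.2.4.1 agree. Protocol Section 4.1 names only SAEs and potential AESIs for the calls, without distinguishing groups.

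**Day 37.** The Group 3 list (Section 8.1.6.3) includes "Review and record AEs". The Day 37 lists for Groups 1A, 1B, 2A and 2B do not. A footnote to each of Tables 5-9 says AEs are gathered at every clinic visit up to Day 51, yet none of those tables marks the AE row in the Day 37 column.

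**The concern.** The safety tables set each antibiotic group beside AV7909 alone, and the secondary safety objective concerns giving vaccine and antibiotic together. Events before Day 8 occur on antibiotic only. They enter the Group 1 and 2 columns, while the Group 3 column cannot hold any. This happens even if every site follows the plan perfectly, and it always works against the antibiotic groups.

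The planned pre-vaccination table does not let a reader undo it. SAP Section 8.1.2 counts a participant once per preferred term and once per organ class. Someone with the same event on Day 5 and on Day 20 is one participant in the Day 51 table and one in the pre-vaccination table. Subtracting would delete the event that followed vaccination.

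The call and Day 37 wording raises a different problem. Section 8.1 gives each group its own schedule, so conflicting instructions leave room for groups to be questioned differently.

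**Working it through.** Safety is descriptive, so the plan states no figure that could be reproduced here.

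**1. Window length.** Start days come from Protocol Section 9.2 and the end is Day 51. Length = 51 - start + 1.
- Group 2: 51 - 2 + 1 = 50 days; 50/44 = 1.14
- Group 1: 51 - 4 + 1 = 48 days; 48/44 = 1.09
- Group 3: 51 - 8 + 1 = 44 days

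**2. Effect on incidence.** Assumptions: constant hazard, the same in all groups, and a 44-day incidence p of 20-80%. With L days, incidence = 1 - (1 - p)^(L/44). For p = 0.40: 1 - 0.60^(48/44) = 0.427 and 1 - 0.60^(50/44) = 0.440. The comparison figure is the 95% half-width for a difference at the planned 70 versus 70, 1.96 × sqrt(2p(1 - p)/70).

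| Assumed p, 44 days | Group 1, 48 days | Group 2, 50 days | Added points, G1 / G2 | Half-width, points |
|---|---|---|---|---|
| 20% | 21.6% | 22.4% | 1.6 / 2.4 | 13.3 |
| 40% | 42.7% | 44.0% | 2.7 / 4.0 | 16.2 |
| 60% | 63.2% | 64.7% | 3.2 / 4.7 | 16.2 |
| 80% | 82.7% | 83.9% | 2.7 / 3.9 | 13.3 |

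**3. Twelve months.** Length = 388 - start + 1, giving 387 (Group 2), 385 (Group 1) and 381 (Group 3), or ratios of 1.02 and 1.01 to Group 3. The unequal start hardly matters at that horizon.

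**4. Calls, side by side.**

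| Group | Footnote names AEs | AE row marked at calls | Section 8.1.7 |
|---|---|---|---|
| 1A, 1B, 2A | yes | yes | AEs included |
| 2B, 3 | no | yes | AEs included |

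If the footnotes were applied literally, non-serious AEs from Day 52 to Day 388 (388 - 52 + 1 = 337 days) would be sought in 1A, 1B and 2A but not in 2B or 3. That affects the 12-month table and leaves the Day 51 table untouched. The split runs through Group 2, so it is not antibiotic versus vaccine alone.

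**5. Day 37, side by side.** The step list has an AE review in Group 3 only. The general footnote covers all five groups, and the schedule mark is absent in all five. Group 2A also has AEs recorded on Day 38 (Section 8.1.4.13). If the lists were followed literally, Group 3 would be asked more, which is the opposite direction to item 1.

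**The case against.** A reader might infer that AEs are ascertained differently by arm and that TEAE rates are therefore not comparable with AV7909 alone. The documents do not support that.

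- **Calls.** Tables 8 and 9 mark the AE row at the safety calls. Their footnotes do not say that only SAEs and AESIs are collected, and they defer to the common script in Section 8.1.7. Section 4.1 omits AEs for every group alike.
- **Day 37.** The general footnote covers the visit in every group. The antibiotic-group lists still review the e-diary, concomitant medication and ongoing vaccination reactions. Section 8.3.3 allows a symptom-directed examination in every group when needed. All groups have AEs reviewed on Day 51, and Section 9.2 records events by when they occurred.
- **Window.** The start day follows directly from the endpoint, and Group 3 has no product before Day 8. Solicited reactions are already summarised after each vaccination in all groups, and the AE listing shows start dates. No safety test is planned.
- **Antibiotic-only columns.** Protocol Section 10.6 lists them. But Section 10.3 and SAP Section 3.2 classify participants by treatment received, so these columns most naturally hold people who never reached vaccination. They do not split one participant's events by period, and SAP Section 3.2 groups the Safety Population only as Groups 1, 2 and 3.

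Most of this stands. It reduces the call and Day 37 points to contradictions in wording. It does not remove the window offset, because a listing is not a comparative table and the pre-vaccination table cannot be subtracted.

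**Conclusion.** This is a cheap improvement, not a defect in the endpoint. The unequal window is certain: 50 and 48 days against 44. Its size is not certain. The 1.6-3.2 points (Group 1) and 2.4-4.7 points (Group 2) rest on an assumed 20-80% incidence and a constant hazard. The true rate before vaccination may be lower than afterwards, or higher when antibiotics start. Either way the offset is well inside the 13-16 point half-width, but it has a fixed direction that more data would not average out.

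The call footnotes, Section 4.1 and the Day 37 lists are internal contradictions to reconcile. They would become real ascertainment differences only if sites followed the narrower text, which the documents do not show. In that case the call wording would harm only the 12-month TEAE summary.

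**What to change.** 1. Keep the endpoint. Add to SAP Section 8.1.2 or 8.1.3 one table of TEAEs by organ class and preferred term, with onset from first vaccination to Day 51, for all groups: 51 - 8 + 1 = 44 days each. State how onset on Day 8 is handled (by clock time where recorded), because Groups 1A and 2A are vaccinated that evening.
2. Align the Table 8 and Table 9 call footnotes and Protocol Section 4.1 with Sections 8.1.7 and 9.2.
3. Add the AE review to the Day 37 lists for Groups 1A, 1B, 2A and 2B, and mark it in the Day 37 column of Tables 5-9.

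The cost is one extra table and a few lines of wording. Sample size, endpoints and visit schedule stay as they are.

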8.1.6.1. Group 3: Day 8 – Vaccination #1

1. Review eligibility.
2. Assess vital signs (seated/semi-recumbent blood pressure, heart rate, respiratory rate and temperature).
3. For WOCBP, collect and perform UPT (prior to AV7909 vaccination). Positive UPTs will be confirmed with a serum pregnancy test. All confirmed pregnancies in participants who receive at least one dose of AV7909 or doxycycline and where conception occurs prior to 12 months after last receipt of either IP will be followed to outcome.
4. Perform symptom-directed PE.
5. Reassess concomitant medications.
6. Administer AV7909 vaccination #1.
7. Participants should be monitored for at least 30 minutes following vaccine administration for any adverse effects especially anaphylaxis.
8. Assess vital signs at 30 ± 5 minutes post-vaccination.
9. Before the participant is discharged from the clinic, they will be trained on the use of e-diary (see [Section 8.3.5.1](#)) and given instructions on how the e-diary should be used to record daily temperature, and any local and systemic reactogenicity events after vaccination. Participants will be instructed to use the e-diary on a daily basis for at least seven days postvaccination. If a reaction is not resolved at seven days postvaccination, the participant is to continue completing the e-diary daily until they are symptom free for two consecutive days.
10. Participants will also be given an injection site reaction measurement tool and shown how to use it to measure the size and rate the intensity of certain reactogenicity events associated with vaccination as well as where to enter this in the e-diary.

Any participant who does not have or who does not wish to use their own personal device to access the e-diary will at this time be supplied a hand-held device by the site.

8.1.6.2. Group 3: Day 23 (± 1 d) Vaccination #2

1. Review participant e-diary discussing any symptoms and any use of pain medications.
2. Review and record AEs.
3. Reassess concomitant medications.
4. Perform symptom-directed PE.
5. Assess vital signs (seated/semi-recumbent blood pressure, heart rate, respiratory rate, and temperature).

AV7909 Anthrax Vaccine

IND 014451

Protocol EBS.AVA.210, Version 3.0 (28 October 2019)

6. For WOCBP, collect and perform UPT (prior to AV7909 vaccination). Positive UPTs will be confirmed with a serum pregnancy test. All confirmed pregnancies in participants who receive at least one dose of AV7909 and where conception occurs prior to 12 months after last receipt of IP will be followed to outcome.
7. Review eligibility for continuing vaccination.
8. Administer AV7909 vaccination #2. Participants should be monitored for at least 30 minutes following vaccine administration for any adverse effects especially anaphylaxis.
9. Assess vital signs (seated/semi-recumbent blood pressure, heart rate, respiratory rate, and temperature) at 30 ± 5 minutes post-vaccination.
10. After diary review the participant will be reminded to use the reactogenicity e-diary and injection site reaction measurement tool to capture the adverse events associated with vaccination, as well as to continue entering their temperatures every day. See [Section 8.3.5.1](#) (e-diary).
11. Prior to discharge following vaccination on Day 23, participants will be reminded to return to clinic in two weeks (± 1 day) on Day 37 ± 1 d for the final blood draws for TNA.

8.1.6.3. Group 3: Day 37 (± 1 d) – Blood Draw for TNA

The Day 37 Visit may shift by ± 1 d.

1. Review e-diary entries with participants, discussing any changes in health status and the use of concomitant medication as well as any vaccination reactions if still ongoing.
2. Review and record AEs.
3. Record concomitant medications.
4. Conduct symptom-directed PE (if necessary).
5. Collect blood sample for TNA assessment.

8.1.6.4. Group 3: Day 51 (± 1 d) – Final In-Clinic Study Visit

1. Perform complete PE.
2. Review e-diary entries with participant and collect hand-held device.
3. Review and record AEs.
4. Record concomitant medications.
5. Measure vital signs (seated/semi-recumbent blood pressure, heart rate, respiratory rate and temperature).
6. For WOCBP, collect and perform UPT. Positive UPTs will be confirmed with a serum pregnancy test. All confirmed pregnancies in participants who receive at least one dose of any IP and where conception occurs prior to 12 months after last receipt of any IP will be followed to outcome.
7. Collect blood sample for hematology.

AV7909 Anthrax Vaccine

IND 014451

Protocol EBS.AVA.210, Version 3.0 (28 October 2019)

8. Collect blood sample for serum chemistry.
9. Collect blood sample for TSH & autoantibody determination.
10. Collect urine sample for urinalysis.

8.1.7. Quarterly Safety Follow-up Phone Calls

Following the last scheduled vaccination, the site will conduct quarterly safety follow-ups in which participants are contacted by phone at 3 months (Day 114 ± 14 d), 6 months (Day 205 ± 14 d), 9 months (Day 296 ± 14 d) and 12 months (Day 388 ± 14 d). These phone contacts will be scheduled to key off the participant's actual or, if missed, target Day 23 visit (intended last vaccination day) so that all participants (even those failing to receive both vaccinations but who are followed for safety only) are contacted 3 months after their target Day 23.

The following assessments will be performed over the phone at the 3 months (Day 114 ± 14 d), 6 months (Day 205 ± 14 d), 9 months (Day 296 ± 14 d) and 12 months (Day 388 ± 14 d) contacts:

- Assess and document, AEs, SAEs and potential AESIs (refer to [Section 9.3](#))
- For WOCBP, confirm continued use of an adequate method of contraception and inquire about any possible pregnancies (refer to [Section 9.4](#))
- If an AE, SAE and/or an AESI is reported, record any associated medications
- Review the status of ongoing AEs/SAEs/AESIs to update the resolution status

During the telephone calls, the staff member is to inquire about and record in source documentation any AEs and SAEs occurring since either the Day 51 visit or the previous phone contact. Any occurrence of SAEs will be reported to Emergent immediately as specified under [Section 9.3](#) and followed up per procedures described in [Section 9.7.2](#). If an SAE has occurred, it will be recorded on the AE eCRF with any medications taken also recorded on the appropriate eCRF.

During the telephone calls, the staff member will also attempt to elicit and record in source documentation any information on AEs of potential autoimmune etiology. If the condition is a diagnosed or suspected AESI, the staff member may refer the participant to the PI or designee for further phone evaluation if needed; based on initial assessment of potential AESI, the participant will be asked to return for an unscheduled clinic visit for evaluation (refer to [Section 8.1.9](#)) and to provide a blood sample for autoantibody testing and/or TSH assessment (if applicable). The PI or designee will obtain records confirming the diagnosis or refer the participant to a medical specialist for additional clinical and diagnostic testing and follow up until the diagnosis is ascertained. The potential AESI will be reported to Emergent immediately as specified in [Section 9.3](#) and followed up per procedures described in [Section 9.7.2](#). Only after the DSMB has assessed the case as a confirmed AESI will the PI or designee record the occurrence of the AESI on the AE eCRF with any medications taken also recorded on eCRFs. The medical monitor or designee will direct the completion of the AE eCRF when communicating the DSMB assessment outcome(s) to the PI or designee.

In the event the site is unable to reach the participant by telephone at any of the interim safety follow-up calls at 3 months (Day 114 ± 14 d), 6 months (Day 205 ± 14 d), 9 months (Day

AV7909 Anthrax Vaccine

IND 014451

Protocol EBS.AVA.210, Version 3.0 (28 October 2019)

296 ± 14 d) and 12 months (Day 388 ± 14 d), at least three phone contact attempts must be made before the site documents that the participant was unable to be reached. The contact attempts will be spaced at least one week apart. Failure to reach the participant at one of the interim safety follow-up time points does not preclude contact attempts at the next scheduled safety follow-up time point. Procedures for the final 12-month follow-up call are described in [Section 7.4](#).

